11.1.3 Retrospective cohort

As part of algorithm development we will perform additional analyses on the retrospective cohort. These will include exploring specific subgroups (obstetric, gastro-intestinal, emergency surgery, trauma) and examining treatment rates (e.g. rates of tranexamic acid use in post-partum haemorrhage). Results of these more detailed analyses will be compared with previously published data and current clinical guidelines.

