2 LAY SUMMARY

Bleeding affects up to 40% of all trauma patients, up to 30% of all surgery patients and is one of the commonest causes of death for women giving birth. The presentation and features of bleeding are

different between patients – in some cases bleeding is very obvious to recognise, but in other cases bleeding is more “hidden”, for example in the stomach. Bleeding must be stopped promptly to prevent severe illness or death.

Many studies have shown differences in how patients who bleed are treated. There is also variation in how individual patients respond to the same treatment, with some patients doing better than others. Understanding how variation in practice and patient characteristics affect outcomes will help us design and test improvements in care.

Patients in hospital have regular tests that measure levels of the different types of cells in their blood and its ability to clot. For example, a drop in red blood cells can indicate that patients have suffered bleeding. More advanced blood tests are available that can provide more detailed information on why patients are bleeding and what treatments might be most effective.

This study aims to develop a real-time, hospital-wide digital system to identify patients in hospital who have suffered from bleeding and test whether this system could be used in the future to potentially identify patients to recruit into trials of new treatments or blood tests.

To do this, we will:

- Assemble a panel of experts to identify criteria (for example, specific blood test results and drug prescriptions) that could indicate a patient has suffered from bleeding
- Use historical electronic patient records to test how well these criteria identify patients who have received treatments for bleeding (blood transfusion)
- Develop and refine a web-based digital system where the most useful criteria can be applied in “real-time” to identify bleeding patients
- Test how well the digital platform identifies bleeding patients
- Test whether a significant number of patients identified by the digital platform are willing to allow their routine blood samples tested for blood clotting and endothelial factors.

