8.1.1 Retrospective cohort

Inclusion Criteria

- Adults aged between 16 and 110
- Admitted to hospital (OUH) or attended the emergency department between 1/3/2011 to 31/8/2022

Exclusion Criteria

- Patients who inform us directly that they do not wish their records used in this research study
- Patients who have completed the NHS Opt-out.

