9 PROTOCOL PROCEDURES

9.1 Algorithm development and validation

- Conduct a modified Delphi process using a panel of clinical experts to identify a set of starting criteria (algorithm) e.g. transfusion request or absolute/drop in Hb. In the first instance, we will aim to agree broad criteria that maximise the sensitivity of the algorithm.
- The Clinical Data Warehouse (CDW) is a digital resource within the Oxford University Hospitals NHS Trust (OUH) that will provide up to 10 years of retrospective anonymised patient data to the study. This dataset will comprise demographics and diagnostic/therapeutic codes, hospital locations, admission/discharge timings as well as laboratory results, radiology reports, blood product usage and operative management and outcomes. All data will be time-stamped.
- Using this retrospective patient data, we will develop an algorithm by mapping criteria identified by the Delphi process to routinely-collected data sources. We will combine these mapped criteria into a single algorithm to identify bleeding patients. We will assess its sensitivity to identify patients who have received treatments/investigations for bleeding (e.g. urgent endoscopy, prescription of tranexamic acid, blood transfusions). We will calculate basic demographics (e.g. age, mortality rates) for the patient cohort and compare these to previously published data e.g. from the Trauma Audit Network (TARN) audit. We will also look at how individual criteria overlap to see whether we can identify any redundancy in the list of data sources.
- Sources of patient data required by the algorithm will be integrated into a “real-time” digital platform by processing HL-7 messaging from individual hospital IT systems. This will expand on a pre-existing software platform (developed for the HAVEN Study, <https://ora.ox.ac.uk/objects/uuid:322561c7-866e-4c1e-bcc1-65da4da477fb>) which listens to hospital wide computer systems, integrating relevant data into a real-time research database.
- Using the real-time database, we will implement the algorithm on a lightweight web interface (R Shiny). The interface will include the ability for users to input additional data from the notes review (details below).

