11.1.2 Descriptive statistics

We will calculate summary statistics (e.g. demographics, treatments, mortality,) for both the retrospective and prospective cohorts identified by the algorithm.

For continuous variables we will use the median/interquartile range; for binary or categorical variables we will use the proportion. Confidence intervals for proportions were calculated using the Pearson-Klopper method. We will be able to make compare event rates with previously published data (UK, USA, Europe).

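### Treatment rates summarised in the algorithm-identified cohort may be biased for any treatment that is itself a selection criterion, so their comparison with external rates is not interpretable

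*Protocol*

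**What the plan says.** Section 11.1.2 fixes the denominator of the descriptive summaries, which expressly include treatments. They are calculated "for both the retrospective and prospective cohorts identified by the algorithm". The same section then says that event rates will be compared with previously published data.

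Section 9.1 describes the criteria from which the algorithm starts: "starting criteria (algorithm) e.g. transfusion request or absolute/drop in Hb". The first of these examples marks a treatment; the second is a laboratory finding. The Lay Summary has an expert panel "identify criteria (for example, specific blood test results and drug prescriptions) that could indicate a patient has suffered from bleeding", without naming any drug. Section 9.1 also judges retrospective sensitivity by how well the algorithm captures patients who received treatments or investigations for bleeding, tranexamic acid and transfusion among them.

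Section 11.1.3 goes further on the retrospective side: "As part of algorithm development we will perform additional analyses on the retrospective cohort". These include "examining treatment rates (e.g. rates of tranexamic acid use in post-partum haemorrhage"), and "Results of these more detailed analyses will be compared with previously published data and current clinical guidelines". It does not say whether the subgroups are drawn from the algorithm-identified patients or from the whole retrospective cohort. Section 8.1.1 defines the latter without any bleeding criterion: "Admitted to hospital (OUH) or attended the emergency department between 1/3/2011 to 31/8/2022".

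**The concern.** A bleeding patient who received a treatment that serves as a criterion enters the cohort because of it. A bleeding patient who did not receive it enters only if some other criterion fires. The denominator of the treatment rate then depends on the treatment being counted.

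Transfusion is the clearest case, because a transfused patient would ordinarily have a transfusion request. Using capture of treated patients as the measure of sensitivity pulls the same way: a bleeder who received no treatment or investigation does not count towards it. This is separate from whether that sensitivity measure is sound. A better reference standard would leave the treatment-rate denominator as it is.

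At stake is the external comparison. The background section gives variation in treatment and uneven uptake of research findings as reasons for the work. If untreated bleeders are preferentially missing, under-treatment is the signal most easily hidden. The protocol states no safeguard.

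**Working it through.** **The plan's own figure.** Section 11.2.2 expects about 250 bleeding events in the first three-month period and assumes 80% sensitivity: 250 × 0.80 = 200 records to review. This reproduces exactly. It is the only sensitivity figure in the protocol, it is stated for the prospective phase, and no positive predictive value comes with it. It is borrowed here for illustration.

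**Inputs.**
- S = 0.80, overall sensitivity (section 11.2.2).
- t, the true treatment rate among bleeders: not in the protocol; 30% and 40% are assumed below.
- s1 and s0, the probabilities that treated and untreated bleeders are flagged: not in the protocol; s1 is varied from 0.80 to 1.00. Since S = t·s1 + (1 − t)·s0, s0 follows.
- PPV, the share of flagged patients who truly bled, and f, the treatment rate among false positives: not in the protocol; PPV is taken as 0.80 or 0.60 and f as 0 or 1.

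**Step 1: flagged true bleeders only.** The treatment rate is t·s1 / (t·s1 + (1 − t)·s0) = t·s1 / S. With t = 40%:

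| s1 | s0 | Rate among flagged bleeders | Ratio to truth |
|---|---|---|---|
| 0.80 | 0.800 | 0.40 × 0.80 / 0.80 = 40% | 1.00 |
| 0.90 | 0.733 | 0.40 × 0.90 / 0.80 = 45% | 1.125 |
| 1.00 | 0.667 | 0.40 × 1.00 / 0.80 = 50% | 1.25 |

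Because s1 cannot exceed 1, the ratio cannot exceed 1/0.80 = 1.25 at this sensitivity. At t = 30% the same limit gives 0.30 / 0.80 = 37.5%. If flagging is unrelated to treatment, there is no bias among bleeders.

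**Step 2: add false positives.** The rate in the whole flagged cohort is PPV × (t·s1 / S) + (1 − PPV) × f. With t = 40% and s1 = 1:

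| PPV | f | Rate in flagged cohort | Effect |
|---|---|---|---|
| 0.80 | 0 | 0.80 × 50% = 40% | inflation cancelled |
| 0.60 | 0 | 0.60 × 50% = 30% | reversed |
| 0.80 | 1 | 0.80 × 50% + 0.20 × 100% = 60% | enlarged |

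Section 9.1 wants broad criteria that maximise sensitivity, with later refinement for specificity, so false positives are expected by design. For the same true rate of 40%, the reported figure ranges from 30% to 60% over these assumed values.

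**The case against.** The strongest reply is that section 11.1.3, where the guideline comparison sits, names only the retrospective cohort, which section 8.1.1 defines as all adult admissions and emergency department attendances. Section 9.1 says the dataset holds diagnostic codes, so a code-defined post-partum haemorrhage denominator is compatible with the text. This stands. The algorithm-selected reading of 11.1.3 is plausible after 11.1.2, but it is not stated.

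Nor is tranexamic acid a stated criterion. Section 9.1 names it among the treatments used to assess sensitivity, and only the unspecified drug prescriptions of the Lay Summary could make it one. The panel has yet to settle the criteria. This also stands, and it is why transfusion, not tranexamic acid, carries the point.

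The analyses are descriptive. Treatment rates are not among the outcome measures in section 6, section 11.4 has no decision points, and a statistical analysis plan is to be finalised before any analysis. That limits the weight of the point but does not remove it, because 11.1.2 itself fixes the denominator as the algorithm-identified cohorts. Section 9.1's planned look at how criteria overlap would show some of the dependence, but it does not change that denominator.

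Three stronger readings are tempting and unsupported:
- **That the rates are inflated.** Step 2 shows that false positives can cancel or reverse the effect, so the direction in the flagged cohort is not known.
- **That the inflation could be much larger than 1.25-fold.** That needs lower sensitivity than the protocol assumes. If every treated bleeder were flagged and other criteria caught only half of the untreated, at t = 40% the sensitivity would be 0.40 + 0.60 × 0.50 = 70%, not 80%.
- **That mortality comparisons shift in the same way.** Death is not given as a criterion, and the protocol offers nothing from which its relation to being flagged could be derived.

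**Conclusion.** The point holds for section 11.1.2 and for any treatment that ends up as a criterion. Among true bleeders the rate is biased upward by at most a factor of 1.25 if sensitivity is 80%, and by nothing if flagging does not depend on the treatment. In the flagged cohort as a whole, size and direction are both unknown. That is enough to make comparison of such a rate with published figures uninterpretable. For section 11.1.3 the conclusion, including the guideline comparison, is conditional on its subgroups being taken from algorithm-identified patients.

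The conclusion assumes that a treatment marker such as a transfusion request survives into the algorithm, that the event rates compared in 11.1.2 include treatment rates, and that the 80% figure carries over from the prospective phase. True treatment rates and positive predictive values are illustrations. The consequence is confined to secondary descriptive results: the target of 200 correctly identified patients with 40 consenting is untouched. This is a worthwhile, inexpensive improvement and not a threat to the study.

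**What to change.** In section 11.1.2, and in 11.1.3 where it applies, state that each treatment rate to be compared externally is computed in one of two ways:
- in a cohort flagged by the algorithm with that treatment, its request and its prescription left out of the criteria; or
- in a subgroup defined by diagnosis codes, such as coded post-partum haemorrhage.

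Show the full-algorithm rate only alongside, labelled as treatment-selected. In 11.1.3, add one sentence saying how each subgroup is identified; if diagnosis coding is already intended, that sentence settles the example there.

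The cost is wording, one re-run per treatment on data already held, and a smaller denominator. The coded-subgroup option suits the retrospective data: section 9.2 destroys the records of prospective patients who never meet the criteria, so there the leave-out run is the practical choice. It needs only the flagged patients, provided that the criteria act as alternatives.

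The leave-out run removes the direct dependence on the treatment. It does not remove false positives, nor any tendency of the remaining criteria, such as a haemoglobin drop, to pick out patients who are more likely to be treated. The report should say so.

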11.2 Sample Size Determination

11.2.1 Retrospective data

The retrospective database will contain up to 1,750,000 patient admissions over ten years (based on an estimate of 175,000 admissions to Oxford University Hospitals NHS Foundation Trust each year).

11.2.2 Prospective data

Up to 87,500 records will be screened by the digital platform to identify those who may have bled over 2 three-month periods.

In the first three-month period, research nurses will review electronic records of patients with bleeding (identified by the algorithm), we estimate around 250 will experience a bleeding event. Assuming the algorithm has a sensitivity of 80%, we plan to review 200 electronic records.

In the second three-month prospective period, research nurses will approach patients for consent. Based on the assumption that 200 patients will also be identified by the algorithm in this period, we will aim for at least 40 (20%) of patients to consent to their participation.

We will assess the efficacy of the sample retention process being used by the study. This will include the number of samples successfully retained, the number of additional clotting laboratory resulted gained from these samples and any feedback from the laboratory staff regarding challenges they faced.

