3 SYNOPSIS

Study Title	RE-BLEED: A digital platform for identifying bleeding patients: a feasibility study
Internal ref. no. / short title	RE-BLEED
Study registration	The study will be registered on clinicaltrials.gov
Sponsor	University of Oxford
Funder	Oxford BRC
Study Design	Study incorporating database analysis, cohort observation and laboratory study
Study Participants	Patients with actual or suspected acquired bleeding
Sample Size	
Retrospective data Up to 1,750,000 patient admissions (up to 10 years of admissions)
 
Prospective data Up to 87, 500 will be screened by the digital platform to identify those who may have bled during the six-month recruitment period. Research nurses will review

	electronic records of patients with potential bleeding (identified by the digital platform), with the aim of gaining consent from at least 50 in the last three months of the study.		
Planned Study Period	1/10/2021 to 31/8/2023		
Planned Recruitment period	Retrospective data from the period: 1/3/2011 to 31/8/2022 Prospective study: 1/10/2021 to 31/8/2023		
	Objectives	Outcome Measures	Timepoint(s)
Primary	To test whether a digital platform can efficiently identify patients who have suffered a bleeding event and are willing to consent for the routine blood samples to be used in research.	At least 200 patients correctly identified as having suffered bleeding, of which 40 (20%) provide consent	End of study
Secondary	
 1. To conduct a Delphi process with an expert panel to identify criteria that could be applied in the electronic patient record to identify patients with acquired bleeding 2. To use 10 years' of retrospective data to map bleeding criteria to appropriate data fields within the electronic patient record data sources 3. To encode bleeding criteria into a real-time "algorithm" and display results within a digital web-based platform 4. To measure and refine the accuracy of the algorithm, by 	
 1. List of bleeding criteria 2. Bleeding criteria mapped to appropriate data fields on the electronic patient record 3. Digital platform capable of identifying bleeding patients in real-time 4. Algorithm accuracy before/after refinement 5. List of unique challenges faced by the laboratory team during blood sample retention and analysis 6. Numbers of samples retained and additional blood clotting and endothelial factor results captured from the retained samples. 	End of study

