6 OBJECTIVES AND OUTCOME MEASURES

Objectives	Outcome Measures	Timepoint(s) of evaluation of this outcome measure (if applicable)
Primary		
To test whether a digital platform can efficiently identify patients who have suffered a bleeding event and	At least 200 patients correctly identified as having suffered bleeding, of which 40 (20%) provide consent	End of study

are willing to consent for the routine blood samples to be used in research.
		

Secondary
		

 1. To conduct a Delphi process with an expert panel to identify criteria that could be applied in the electronic patient record to identify patients with acquired bleeding 2. To use 10 years’ of retrospective data to map bleeding criteria to appropriate data fields within the electronic patient record data sources 3. To encode bleeding criteria into a real-time “algorithm” and display results within a digital web-based platform 4. To measure and refine the accuracy of the algorithm, by manual review of free-text notes of patients identified as bleeding 5. Assess the feasibility of sample sequestering by the lab 6. Assess the feasibility of performing blood clotting and endothelial factor analysis on the sequestered samples. 	
 1. List of bleeding criteria 2. Bleeding criteria mapped to appropriate data fields on the electronic patient record 3. Digital platform capable of identifying bleeding patients in real-time 4. Algorithm accuracy before/after refinement 5. List of unique challenges faced by the laboratory team during blood sample retention and analysis 6. Numbers of samples retained and additional blood clotting and endothelial factor results captured from the retained samples. 	
End of study

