- Research nurses will use the interface to identify (up to 200) patients who are potentially bleeding and review their free-text notes in the electronic patient record, notifying attending clinicians when there is no documentation of bleeding. Using the additional clinical information in patients’ notes, the nurses will record whether they agree with the output of the algorithm. Where the algorithm has incorrectly identified patients as having bled, the nurses will record the reasons for bleeding based on the clinical information in the notes.
- The expert panel will review the results of the notes review and refine the algorithm to increase its specificity.
- The expert panel will not have any access to confidential patient information.

9.2 Consent patients identified by system for use of surplus routine blood samples in research analysis.

In the final three months of the study, we will prospectively test the accuracy of the algorithm and the feasibility of using the real-time platform for consenting patients to use their data and routine blood samples for future research.

When the algorithm identifies that a patient has met the criteria for bleeding, the platform will:

- Allocate the patient a RE-BLEED study ID.

- Electronic Hospital Record (EHR) data for this entire encounter will be retained in the study database and when the encounter ends the record will be pseudo-anonymised.
- A notification will be sent to the main hospital laboratory requesting that their (left-over) blood samples, once all clinical testing has been completed as part of routine clinical care, be retained for use in the study, pending patient consent. Where consent is not given, the samples will be destroyed as per local protocols.

In order to be able to screen all patients in the hospital, the system must collect data for all adult patients from their admission to their discharge. The records of adult patients admitted to the hospital who do not meet the eligibility at any point during their admission will be destroyed at the point they are discharged from hospital.

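### Section 11.2.2 derives 200 as expected true positives but uses it as a count of flagged patients, with no positive predictive value linking the two

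*Protocol*

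**What the plan says.** **Protocol 11.2.2, first period.** Of the patients in this period, "we estimate around 250 will experience a bleeding event". The text goes on: "Assuming the algorithm has a sensitivity of 80%, we plan to review 200 electronic records".

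**Protocol 11.2.2, second period.** The consent target starts from the same figure: "Based on the assumption that 200 patients will also be identified by the algorithm in this period", with at least 40 (20%) to consent.

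**Protocol 3 and 6, primary outcome.** "At least 200 patients correctly identified as having suffered bleeding, of which 40 (20%) provide consent". The only timing given is the end of the study.

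**What is reviewed.** Section 9.1 describes the review this way: "Research nurses will use the interface to identify (up to 200) patients who are potentially bleeding". The synopsis likewise has nurses reviewing "electronic records of patients with potential bleeding (identified by the digital platform").

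**False positives are expected.** On the starting criteria, section 9.1 says "we will aim to agree broad criteria that maximise the sensitivity of the algorithm". It also tells nurses what to record for wrong flags ("Where the algorithm has incorrectly identified patients as having bled") and has the expert panel refine the algorithm afterwards to raise specificity. No PPV, specificity or false-positive rate is given anywhere in the protocol.

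**When accuracy and consent are assessed.** Sections 7 and 9.2 place the prospective accuracy test and the consent work in the final three months. Section 11.4 states that there are no decision points.

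**The concern.** Sensitivity is the share of true bleeders that the algorithm finds. Multiplied by the number of bleeders, it gives true positives. It says nothing about how many non-bleeders are flagged as well, so it cannot give the number of records to open or of patients flagged. Section 11.2.2 nevertheless moves straight from sensitivity to a number of records.

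The same 200 then does three jobs: flagged records to review in period 1, patients found by the algorithm in period 2, and confirmed bleeders in the primary outcome. These agree only if there are no false positives, and section 9.1 plans for false positives.

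Two things are at stake. The first is workload: if 200 confirmed bleeders are wanted, more than 200 flags must be assessed, and the protocol does not say so. The second is interpretation: 40 consents out of 200 flagged patients and 40 out of 200 confirmed bleeders are different results. Both would be reported as 20%.

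**Working it through.** **Inputs from the protocol.** About 250 bleeding events in a three-month period, sensitivity 80%, 200 records to review, 200 patients found by the algorithm in period 2, and 40 (20%) consents (all 11.2.2); at least 200 confirmed bleeders with 40 consents (3 and 6); up to 87,500 records screened over two three-month periods (11.2.2).

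**Assumption.** PPV is not stated, so a range is shown.

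**1. Reproduce the plan's figure.** True positives = bleeders x sensitivity = 250 x 0.80 = 200. The arithmetic is right, and the result is a count of true positives.

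**2. Confirmed bleeders among 200 reviewed flags.** Confirmed = 200 x PPV.

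**3. Flags to assess to find 200 confirmed bleeders.** Flags = 200 / PPV, rounded up.

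**4. Consent rate needed among confirmed bleeders for 40 consents, if only 200 patients are flagged in period 2.** Rate = 40 / (200 x PPV).

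| Assumed PPV | Confirmed among 200 flags | Flags for 200 confirmed | Consent rate needed for 40 |
|---|---|---|---|
| 100% | 200 | 200 | 20% |
| 90% | 180 | 223 | 22% |
| 80% | 160 | 250 | 25% |
| 70% | 140 | 286 | 29% |
| 50% | 100 | 400 | 40% |

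The three uses of 200 coincide only in the first row.

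**5. Is the assumed range unreasonable?** Split the 87,500 records evenly (an assumption), giving 43,750 per period, of which 250 are bleeders and 43,500 are not. False positives = 43,500 x (1 - specificity), and PPV = 200 / (200 + false positives).

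- Specificity 99.9%: 43.5 false positives; PPV = 200 / 243.5 = 82%.
- Specificity 99.5%: 217.5 false positives; PPV = 200 / 417.5 = 48%.

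Bleeders are about 0.6% of records (250 / 43,750), so even a very specific algorithm can have a PPV well below 100%. These specificities are illustrative, not the protocol's.

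**6. What the 200-record review can deliver.** It would estimate PPV usefully. The exact 95% interval is 42.9% to 57.1% for 100/200 confirmed, and 63.1% to 76.3% for 140/200.

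**The case against.** The strongest defence is that the 200 means true positives throughout. Section 11.2.2 speaks of patients with bleeding whom the algorithm has found, it carries the figure into period 2, and the primary outcome counts correct identifications. On that reading the target agrees with its derivation. This stands as far as the target goes. It does not rescue the review figure: nurses cannot pick out true positives before reading the notes, and section 9.1 describes the reviewed patients as only potentially bleeding.

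It is also fair to say that PPV is something a feasibility study sets out to learn, that accuracy before and after refinement is already a secondary outcome, and that exact intervals are planned in 11.1.2. The synopsis also links nurse review to the consent approach, which narrows the gap between flagged and confirmed patients. It does not say that only confirmed patients are approached.

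A reader might go further in two ways, and the protocol supports neither.

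- **That the primary target requires a PPV of 100%.** This would follow only if period 2 stopped at 200 flags. The limit of 200 in section 9.1 applies to the notes review before refinement. The period 2 figure is introduced as an assumption, and nothing caps flags there.
- **That flags from both periods may be pooled.** About 400 flags would make a PPV of 50% enough, so that the required PPV would run from 100% to none depending on the reading. But the outcome nests the 40 consents within the 200, consent is sought only in the final three months, and the accuracy test is placed there too. Pooling would add patients flagged before refinement whom section 11.2.2 does not plan to approach.

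**Conclusion.** The point holds in a limited form and should be fixed. The multiplication is correct, but its result is used for a quantity it does not measure. Section 11.2.2 turns expected true positives into a number of flagged records and then bases the consent target on patients found by the algorithm, while sections 3 and 6 base it on confirmed bleeders.

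The size depends on a PPV that the protocol does not state. Over an assumed 90% to 50%, the yield from 200 flags falls short of 200 by 20 to 100 patients, or the flags to assess exceed 200 by 23 to 200. The consent rates of 25% (PPV 80%) and 40% (PPV 50%) apply only if period 2 produces no more than 200 flags.

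The final three months is the most natural counting period, from sections 7, 9.2 and 11.2.2, but this is an inference: the primary outcome gives an evaluation timepoint, not a counting window. With no decision point in 11.4, the consequence is an under-planned review and a feasibility result that is harder to interpret.

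**What to change.** - In sections 3, 6, 9.1 and 11.2.2, label each 200 as flagged or confirmed.
- In 11.2.2, write the chain in full: bleeders x sensitivity = true positives; true positives / PPV = flags. Give an assumed PPV range, informed by the retrospective run where possible.
- Keep the period 1 review at 200 flagged records and state its expected confirmed yield as 200 x PPV.
- Define the primary count as confirmed bleeders among all flags assessed in the final three-month period, with consent counted among those confirmed.
- Report PPV (confirmed / flagged and assessed) and consent among confirmed bleeders as proportions, with the exact intervals already planned in 11.1.2.

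**Cost.** Wording in four sections. The review size and the primary target do not change. The downside is a less favourable stated yield from 200 flags or, if 200 confirmed bleeders are to be found in the final period, a larger stated number of flags to assess: 23, 86 or 200 more than 200 at PPVs of 90%, 70% or 50%.
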